4.5. Study Termination

The Sponsor has the right to terminate this study at any time. Reasons for terminating the study early may include, but are not limited to, the following:

- The incidence or severity of AEs in this or other studies indicates a potential health hazard to patients
- Overall patient enrollment is unsatisfactory
- Poor protocol adherence
- Inaccurate or incomplete data recording
- Good Clinical Practice (GCP) noncompliance
- Study activity is completed (ie, all patients have completed and all obligations have been fulfilled).

[figure not shown]
The Sponsor will notify the PI if a decision is made to terminate the study. Should this be necessary, prematurely discontinued patients should be seen as soon as possible for an EOT visit and safety Follow-up visit.

The PI may be informed of additional procedures to be followed in order to ensure that adequate consideration is given to the protection of the patient's interests. The PI will be responsible for informing the EC of the early termination of the study.

12 December 2018 Page 32 of 72

5. STUDY TREATMENTS

5.1. Description, Storage, Packaging, and Labelling

CONFIDENTIAL

Protocol Reference: BGB-290-106

5.2. Study Treatment Administration

5.2.1. Part 1

Patients should be fasted 1 hour before and 2 hours after the dose. [14C]-pamiparib will be administered orally with approximately 240 mL of room temperature water.

At all times during the study, patients may consume water ad libitum.

Patients will be dosed while seated and will not be permitted to lie supine for 2 hours after administration of [14C]-pamiparib except as necessitated by the occurrence of an AE(s) and/or study procedures.

5.2.2. Part 2

Pamiparib capsules will be dispensed to patients by qualified site personnel at scheduled site visits throughout Part 2 to ensure that patients have an adequate drug supply for administration at home. The patient will be instructed to take the study drug exactly as prescribed, once in the morning and once in the evening at approximately the same time each day.

12 December 2018 Page 33 of 72

Protocol Amendment Version 3.0 Covance Study: 8381180 Protocol Reference: BGB-290-106

Patients will be requested to bring their unused medication to the CRU at each visit. All dosages prescribed and dispensed to the patient and all dose changes including reason for dose changes during the study must be recorded in the eCRF.

CONFIDENTIAL

5.3. **Treatment Compliance**

The following measures will be employed to ensure treatment compliance in Part 1:

- The dose will be administered under the supervision of suitably qualified study site staff.
- Immediately after oral administration, visual inspection of the mouth will be performed on each patient.

In Part 2, patients will self-administer all doses of pamiparib at home. Patients will be asked to record daily timing and dose in a dosing diary, and the dosing diary will be reviewed at site visits to check treatment compliance.

5.4. **Drug Accountability**

The PI (or designee) will maintain an accurate record of the receipt of the study supplies received. In addition, an accurate drug disposition record will be kept, specifying the amount dispensed to each patient and the date of dispensing. This drug accountability record will be available for inspection at any time. At the completion of the study, the original drug accountability record will be available for review by the Sponsor upon request.

In Part 1, empty, used unit dose containers will undergo radioanalysis to determine the amount of any residual radioactivity remaining after dose administration and will be discarded upon satisfactory completion of the compliance and accountability procedures. Any unused assembled unit doses will be retained until completion of Part 1 of the study before being returned to the Sponsor or disposed of by the study site, per the Sponsor's written instructions or site standard operating procedures (SOPs).

In Part 2, all unused pamiparib will be returned to the study site.

At the completion of the study, all unused supplies will be returned to the Sponsor or disposed of by the study site, per the Sponsor's written instructions or site SOPs.

5.5. **Dose Hold and Modification**

The relationship between AEs and pamiparib will be assessed by the PI (or designee). Dosing of pamiparib in Part 2 can be withheld for up to 28 days consecutively.

Criteria for treatment modifications and suggested guidelines for the management of some toxicity related to pamiparib are summarized below. These general guidelines may be modified at the discretion of the PI based on discussions with the Medical Monitor and the best clinical judgment at that time; any decisions should be documented. Any toxicity related to pamiparib should be managed according to standard medical practice.

12 December 2018 Page 34 of 72 A maximum of 2 dose reductions is allowed before the patient must be permanently withdrawn from study drug. Dose levels for pamiparib are summarized in Table 2. Pamiparib should be dose-modified as outlined in Table 3.

CONFIDENTIAL

Protocol Reference: BGB-290-106

Table 2: Dose Levels for Pamiparib

Dose Level	Pamiparib
1	60 mg orally, twice daily
-1	40 mg orally, twice daily
-2	20 mg orally, twice daily

Pamiparib may be dose-reduced for a maximum of 2 dose reductions.

Table 3: Criteria for Modification of Pamiparib Dosing for Related Adverse Events

Toxicity	Recommended Dose Modification ^a		
Hematologic			
Anemia (hemoglobin, Hgb)			
Grade 2 (Hgb < 10 - 8 g/dL)	First occurrence: continue dosing at current dose level		
	Second and subsequent occurrences: hold pamiparib until resolved to ≤ Grade 1 or baseline		
	• If resolved ≤ 14 days, then maintain dose levels		
	• If resolved > 14 days, then ↓ pamiparib by 1 dose level		
Grade 3 (Hgb < 8 g/dL)	Hold pamiparib until resolved to ≤ Grade 1 or baseline		
	• If resolved ≤ 14 days, then maintain dose levels		
	• If resolved > 14 days, then ↓ pamiparib by 1 dose level		
Grade 4 (life-threatening	Hold pamiparib until resolved to ≤ Grade 1 or baseline and		
consequences; urgent intervention indicated)	✓ pamiparib by 1 dose level		
Neutropenia (absolute neutrophil count, ANC)			
Grade 3 (ANC $< 1.0 - 0.5 \times 10^9/L$)	Hold pamiparib until resolved to ≤ Grade 2 or baseline		
	• If resolved ≤ 7 days, then maintain dose levels		
	• If resolved > 7 days, then ↓ pamiparib by 1 dose level		
Grade 4 (ANC < 0.5×10^9 /L)	Hold pamiparib until resolved to ≤ Grade 1 or baseline and		
	✓ pamiparib by 1 dose level		
Febrile neutropenia (ANC < 1.0 ×	Hold pamiparib until resolved and		
10 ⁹ /L with single temperature of > 38.3°C or sustained temperature of ≥ 38°C for > 1 hour)	✓ pamiparib by 1 dose level		

12 December 2018 Page 35 of 72

Toxicity	Recommended Dose Modification ^a		
Thrombocytopenia (platelet count, PI	T)		
Grade 3 (PLT < 50 - 25 × 10 ⁹ /L)	 Hold pamiparib until resolved to ≤ Grade 1 or baseline If resolved ≤ 7 days, then maintain dose levels If resolved > 7 days, then pamiparib by 1 dose level 		
Grade 4 (PLT < 25 × 10 ⁹ /L)	Hold pamiparib until resolved to ≤ Grade 1 or baseline and ↓ pamiparib by 1 dose level		
Renal			
Estimated glomerular filtration rate (MDRD STUDY EQ; www mdrd.com or Appendix 7)			
If $\geq 60 \text{ mL/min/1.73 m}^2$ at baseline: $< 30 \text{ to } 15 \text{ mL/min/1.73 m}^2$ or If $< 60 \text{ mL/min/1.73 m}^2$ at baseline: $\geq 50\%$ reduction from baseline	 Hold pamiparib until resolved to ≥ 60 mL/min/1.73 m² If resolved ≤ 7 days, then maintain dose levels If resolved > 7 days, then ↓ pamiparib by 1 dose level 		
Regardless of baseline: < 15 mL/min/1.73 m ²	Permanently discontinue pamiparib		
Hepatic			
Bilirubin			
Grade 2 (> 1.5 - 3.0 × ULN) Only applies to patients with normal bilirubin at baseline	 Hold pamiparib until resolved to ≤ Grade 1 or baseline If resolved ≤ 7 days, then maintain dose levels If resolved > 7 days, then pamiparib by 1 dose level 		
Grade 3 (> 3.0 - 10.0 × ULN)	 Hold pamiparib until resolved to ≤ Grade 1 or baseline If resolved ≤ 7 days, then maintain dose levels If resolved > 7 days, then pamiparib by 1 dose level 		
Grade 4 (> 10.0 × ULN)	Permanently discontinue pamiparib Note: If Grade 3 or 4 hyperbilirubinemia is due to the indirect (unconjugated) component only, and hemolysis as the etiology has been ruled out as per institutional guidelines (eg, review of peripheral blood smear and haptoglobin determination), then pamiparib by 1 dose level and continue treatment at the discretion of the Investigator in discussion with the Medical Monitor		
Aspartate aminotransferase (AST) and/or alanine aminotransferase (ALT)			
Grade 3 (> 5 and \leq 20 × ULN)	 Hold pamiparib until AST and/or ALT resolved to ≤ 5 × ULN or baseline If ≤ 5 × ULN within 14 days, then pamiparib by 1 dose level If second episode, permanently discontinue pamiparib If persistent for > 14 days, permanently discontinue pamiparib 		
Grade 4 (> 20 × ULN)	Permanently discontinue pamiparib		
Pancreatic	, , ,		
Pancreatitis			
Grade 3 or 4	Permanently discontinue pamiparib		

CONFIDENTIAL

Protocol Reference: BGB-290-106

12 December 2018 Page 36 of 72

Toxicity	Recommended Dose Modification ^a
Cardiac	
Cardiac - Prolonged QTc interval	
QTcF > 500 ms or > 60 ms from the higher of the baseline or predose value	• Obtain triplicate ECGs (2 to 3 minutes apart) ~ 1 hour after initial ECG
	• If mean QTcF > 500 ms, or > 60 ms from baseline value, hold pamiparib until evaluation of ECGs by cardiologist
	 Cardiology evaluation as soon as practical but within 7 days of initial abnormal ECG
	If mean QTcF > 500 ms confirmed by cardiologist, permanently discontinue pamiparib
Cardiac - General	
Grade 3	Hold pamiparib until resolved to ≤ Grade 1 or baseline and
	Ψ pamiparib by 1 dose level
Grade 4	Permanently discontinue pamiparib
Other adverse events	
Grade 3	Hold pamiparib until resolved to ≤ Grade 1 or baseline and V pamiparib by 1 dose level
	No dose reduction required for asymptomatic laboratory abnormalities
Grade 4	Permanently discontinue pamiparib

CONFIDENTIAL

Protocol Reference: BGB-290-106

Abbreviations: ECG = electrocardiogram; MDRD = Modification of Diet in Renal Disease; QTcF = QT interval corrected for heart rate using Fridericia's formula; ULN = upper limit of normal.

12 December 2018 Page 37 of 72

a. Dosing of pamiparib can be withheld for up to 28 days consecutively.

Protocol Amendment Version 3.0 Covance Study: 8381180 Protocol Reference: BGB-290-106

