Patients must be supine for at least 5 minutes before blood pressure, heart rate, and temperature measurements. During the in-house period in Part 1, blood pressure, heart rate, and temperature measurements should be conducted in the morning.

7.2.4. 12-Lead Electrocardiogram

Resting 12-lead ECGs will be recorded after the patient has been supine and at rest for at least 5 minutes at the times indicated in the Schedule of Assessments in Appendix 4.

Single 12-lead ECGs will be repeated once if outside the clinical reference range.

12 December 2018 Page 41 of 72 In the case of an abnormality such as prolonged QT interval corrected for heart rate using Fridericia's formula > 500 msec or > 60 msec from the highest baseline or predose value, new arrhythmia, or other clinically significant finding, ECGs will be recorded in triplicate at least 2 minutes apart.

CONFIDENTIAL

Additional 12-lead ECGs may be performed at other times if judged to be clinically appropriate or if the ongoing review of the data suggests that a more detailed assessment of ECGs is required. The PI (or designee) will perform a clinical assessment of each 12-lead ECG.

7.2.5. **Physical Examination**

Complete and limited physical examinations will be performed at the timepoints specified in the Schedule of Assessments in Appendix 4. A complete physical examination includes a review of the following systems: head/neck/thyroid; eyes/ears/nose/throat; respiratory; cardiovascular; lymph nodes; abdomen; skin; musculoskeletal; and neurological. A limited physical examination includes an assessment of the patient's general appearance, skin, thorax/lungs, cardiovascular, and abdomen.

7.2.6. **Eastern Cooperative Oncology Group**

The ECOG performance status will be evaluated at the times indicated in the Schedule of Assessments in Appendix 4.

7.2.7. **Tumor Assessments**

Tumor imaging (CT or magnetic resonance imaging [MRI], with preference for CT) will be performed at Screening or Part 2 Pre-dose Visit and every 12 weeks (± 7 days) from the time of the Part 2 C1D1. At the PI's discretion, CT or MRI scans may be repeated at any time if PD is suspected.

A CT scan or MRI of the thorax, abdomen, and pelvis plus other relevant evaluations as appropriate will be performed to assess all known disease.

The same imaging technique should be used for each patient throughout the study.

7.3. **End-of-Treatment Visit**

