Protocol Reference: BGB-290-106

- f. **Pregnancy test (in female patients of childbearing potential):** Urine pregnancy test conducted as indicated. A positive urine pregnancy test will be confirmed with a serum pregnancy test.
- g. Dosing: Pamiparib capsules should be administered continuously from Cycle 1 Day 1 (60 mg twice daily), until patients are discontinued from treatment.
- h. CT or MRI scan: Scan to be done every 12 weeks \pm 7 days from the time of Part 2 C1D1.
- i. Vital Signs: Blood pressure, heart rate, and temperature must be measured after the patient has been supine for 5 minutes at Screening.
- j. **ECG** Single 12-lead ECGs will be repeated once if outside the clinical reference range, or there is other clinically significant finding. Repeat ECGs will be recorded in triplicate at least 2 minutes apart. ECGs will be recorded after the patient has been supine for 5 minutes.
- k. **Limited physical examination:** A limited physical examination includes assessment of general appearance and additional examination of symptomatic systems or those affected by the patient's disease. For the follow-up visit, the limited physical examination is only to be done if this visit is conducted whilst the patient is attending the clinic.
- 1. **Follow-up assessments**: only to be conducted if the patient has an ongoing laboratory abnormality at the previous visit that the PI considers to be related to the study drug.

12 December 2018 Page 66 of 72

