10.1.1 Definition of Baseline and Change from Baseline

Baseline for each parameter is in each part defined as the last value measured prior to dosing for that part i.e. Baseline for Part 1 is to be the last value prior to dosing for Part 1 and for Part 2, last value prior to the 1st dose in Part 2, including repeat (vital signs and electrocardiograms [ECGs]) and unscheduled (clinical laboratory parameters) readings (see Section 10.1.2 for definitions of repeat and unscheduled readings). For ECGs taken in triplicate, baseline will be the mean of the last 3 values taken prior to dosing.

Mean change from baseline is the mean of all individual patient's change from baseline values. Each individual change from baseline will be calculated by subtracting the individual patient's baseline value from the value at the timepoint. The individual patient's change from baseline

Statistical Analysis Plan Covance Study: 8381180

values will be used to calculate the mean change from baseline using a SAS procedure such as Proc Univariate.

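### Table 3's QTcF rule triggers the confirmatory triplicate against one reference value and judges the hold against another, leaving a gap when predose exceeds baseline

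*Protocol*

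**What the plan says.** Protocol Section 5.5, Table 3, handles prolonged QTc in stages. The entry condition is "QTcF > 500 ms or > 60 ms from the higher of the baseline or predose value". Meeting it leads to the confirmation step, "Obtain triplicate ECGs (2 to 3 minutes apart) ~ 1 hour after initial ECG". The hold is then judged on that triplicate: "If mean QTcF > 500 ms, or > 60 ms from baseline value, hold pamiparib until evaluation of ECGs by cardiologist". Section 5.5 ties withholding of doses to Part 2.

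Section 7.2.4, which falls under a heading covering both parts, calls for triplicates when QTcF is "> 500 msec or > 60 msec from the highest baseline or predose value, new arrhythmia, or other clinically significant finding". Footnote j of the Part 1 schedule (Appendix 4) repeats that condition. Section 7.2.4 also provides that "Single 12-lead ECGs will be repeated once if outside the clinical reference range". Footnote j of the Part 2 schedule gives no QTcF figure. It says "Single 12-lead ECGs will be repeated once if outside the clinical reference range, or there is other clinically significant finding", and adds that repeats are taken in triplicate.

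The protocol text available does not define which ECG is baseline and which is predose for Part 2. SAP Section 10.1.1 defines baseline for analysis as "the last value measured prior to dosing for that part".

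**The concern.** The first step of a two-step rule is a screen. It should pass on every tracing that the second step could act on. Here the screen measures the rise from the larger of two values and the action step measures it from one of them, so the screen can be harder to satisfy than the action. A tracing may then lie above the figure used for the hold while nothing in the numeric rule obliges anyone to record the triplicate. Because the hold is defined on the triplicate mean, the hold question is not reached through the table for that tracing.

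At stake is the consistent application of a safety action in the treatment phase. Two readers who assign different ECGs to baseline and predose could treat the same tracing differently.

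**Working it through.** **Inputs.** B = baseline QTcF, P = predose QTcF, Q = QTcF on the initial on-treatment ECG, all in ms. The limits of 60 and 500 ms come from Table 3. The plan states no figure to reproduce.

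**Conditions.**
- Triplicate triggered: Q > 500, or Q − max(B, P) > 60.
- Hold number exceeded: Q > 500, or Q − B > 60. The table applies this to the triplicate mean; here the same number is compared with the initial reading.

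**Direction of the mismatch.** Since max(B, P) ≥ B, any reading that triggers the triplicate also exceeds the hold number. The reverse fails when Q ≤ 500, Q ≤ max(B, P) + 60 and Q > B + 60. If P ≤ B, the last two contradict each other. So the gap is exactly:

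P > B and B + 60 < Q ≤ min(P + 60, 500).

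It is empty unless B + 60 < 500, that is, B < 440.

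**Worked values.**

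| B | P | Q | Q − B | Q − max(B, P) | Triplicate triggered | Hold number exceeded |
|---|---|---|---|---|---|---|
| 400 | 430 | 460 | 60 | 30 | no | no |
| 400 | 430 | 461 | 61 | 31 | no | **yes** |
| 400 | 430 | 470 | 70 | 40 | no | **yes** |
| 400 | 430 | 490 | 90 | 60 | no | **yes** |
| 400 | 430 | 491 | 91 | 61 | yes | yes |
| 380 | 400 | 445 | 65 | 45 | no | **yes** |
| 400 | 400 | 461 | 61 | 61 | yes | yes |
| 430 | 400 | 491 | 61 | 61 | yes | yes |
| 430 | 460 | 501 | 71 | 41 | yes (> 500) | yes |

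**Width of the gap.** For P > B and B < 440 the width is min(P + 60, 500) − (B + 60).
- B=400 with P=405, 410, 420 or 430: 5, 10, 20 or 30 ms.
- B=430, P=450: 500 − 490 = 10 ms.
- B=440, P=450: 500 − 500 = 0.

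**Exhaustive check.** Over whole-millisecond values (assumed ranges: B and P 350–470, Q 350–560), 248,430 combinations exceed the hold number without triggering the triplicate. None has P ≤ B, and none triggers the triplicate without exceeding the hold number. The count depends on the ranges chosen and is not a frequency in patients.

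**One common reference.** If both steps use the same value R, both conditions become Q > 500 or Q − R > 60, and the gap is empty. The gap therefore comes only from the mismatch, whichever R is chosen.

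**The case against.** The strongest reply is that the rule has few tracings to miss. Part 1 is a single dose, so there is nothing to hold. The Part 2 schedule places ECGs at the predose visit, before treatment, and at the end-of-treatment visit, after pamiparib has been stopped. The rule therefore acts on unscheduled ECGs, which are taken because someone judged them appropriate, and the investigator assesses each one. This stands, and it limits the practical reach.

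Second, Part 2 schedules one pre-treatment ECG. If both terms mean that reading, as the SAP's per-part baseline would suggest, P equals B and the gap disappears. That is correct, but the protocol does not say so, and the trigger's choice between two values implies that they can differ. The SAP definition governs analysis, not treatment decisions.

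Third, a reading outside the clinical reference range, a clinically significant finding or the investigator's discretion can each lead to further ECGs. Table 3 is also a guideline that the investigator may adapt after discussion with the Medical Monitor. These routes may catch some patients. The reference range is not stated, so a reading such as 445 ms with B=380 and P=400 cannot be assumed to fall outside it.

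A reader might infer that Part 2 has no numeric QTc trigger for triplicates, because its footnote j gives none. The documents do not support that: Section 7.2.4 applies to both parts. Nor is its wording, "> 60 msec from the highest baseline or predose value, new arrhythmia", a different reference from the Table 3 trigger.

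**Conclusion.** The inconsistency is real and minor. Within one row of Table 3, the confirmation step is never more sensitive than the hold step, and it is less sensitive whenever P > B and B < 440 ms. This follows from the two stated conditions and needs no assumption about variability. That the gap occurs in practice rests on baseline and predose being different readings, which the protocol leaves open.

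A reader might infer that a sizeable share of patients with a rise above 60 ms would go unconfirmed. The documents do not support a percentage. They give no within-patient QTcF variability, no expected size of rise and no scheduled on-treatment ECGs in Part 2 to serve as a denominator. A reader might also infer that a patient could meet the hold criterion and be ignored. Strictly, the criterion applies to the triplicate mean, so a single tracing can only exceed the same number. The PK endpoints, which come from Part 1, are not affected.

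**What to change.** Reconcile the trigger and hold steps of Table 3 with Section 7.2.4 and with footnote j of both schedules. State one reference value, naming the reading and the Part it comes from, and use it in both steps, so that any reading above the hold limit also triggers confirmation. Align the Part 2 footnote with Section 7.2.4, including whether an out-of-range ECG is repeated singly or in triplicate. Which reference applies is for the sponsor's clinicians to decide.

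Optionally, SAP Section 10.5.5 could flag QTcF rises above 60 ms against the same reference. The reconciliation does not depend on this.

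The cost is a wording change in the protocol, plus one SAP sentence if the option is taken, and possibly a few more triplicate ECGs.

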10.1.2 Repeat and Unscheduled Readings

Repeat readings occur when the original vital signs or ECG result requires confirmation. Repeat readings are labelled as 'Repeat' in the listings and replace the original readings in all summaries and changes from baseline presentations and calculations. Prior to dosing, all readings taken in addition to the original reading are defined as predose repeats. Postdose repeat readings are defined as readings collected within 15 minutes of the actual time of the original reading. Where results are taken in triplicate and repeated, the last 3 readings are used in all subsequent calculations.

With the exception of predose results described above, unscheduled readings for vital signs or ECGs are defined as readings collected >15 minutes from the actual time of the original reading. Where results are taken in triplicate, the original reading is defined as the first reading of the triplicate. All results not taken at a scheduled timepoint for other data types (eg, clinical laboratory parameters) are unscheduled. Unscheduled readings are labelled as 'Unscheduled' in the listings. Because unscheduled readings are not associated with any scheduled timepoint, they are excluded from all summaries (with the exception that they may be used as baseline, as stated in Section 10.1.1).

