10.5.5 Electrocardiogram

The ECG data will be obtained directly from the 12-lead ECG traces. These data include the QT interval calculated using the Fridericia correction (QTcF), the PR and QT intervals, the QRS duration, and heart rate.

Where ECGs are measured in triplicate (at approximately 2-minute intervals), the mean value will be used in all subsequent calculations. Changes from baseline will be calculated.

Values for ECG parameters outside the clinical reference ranges will be flagged on the individual patient data listings.

Statistical Analysis Plan Covance Study: 8381180 Sponsor Reference: BGB-290-106

The ECG data will be summarized by part. Change from baseline will also be summarized for Part 1.

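### The QTcF triplicate that decides a Part 2 hold or discontinuation enters no ECG summary, mainly because the SAP excludes unscheduled ECGs and Part 2 schedules none during treatment

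*Protocol*

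**What the plan says.** Protocol Section 5.5, Table 3 starts from a QTcF above 500 ms, or more than 60 ms above the higher of the baseline or predose value. The first step is "Obtain triplicate ECGs (2 to 3 minutes apart) ~ 1 hour after initial ECG". Two rules then rest on the triplicate mean: "If mean QTcF > 500 ms, or > 60 ms from baseline value, hold pamiparib until evaluation of ECGs by cardiologist" and "If mean QTcF > 500 ms confirmed by cardiologist, permanently discontinue pamiparib".

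SAP 10.1.2 describes a repeat as a reading taken because the original needs confirming, and lets it replace the original in summaries. It limits this after dosing: "Postdose repeat readings are defined as readings collected within 15 minutes of the actual time of the original reading". Beyond that limit, "unscheduled readings for vital signs or ECGs are defined as readings collected >15 minutes from the actual time of the original reading". The consequence is explicit: "Because unscheduled readings are not associated with any scheduled timepoint, they are excluded from all summaries", with use as baseline the only exception. SAP 10.5.5 says that for triplicates "the mean value will be used in all subsequent calculations", and gives no exemption from the 15-minute rule. It plans ECG summaries by part, with change from baseline summarized for Part 1 only.

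In the Part 2 schedule (Appendix 4), the ECG row is marked at the predose visit and the end-of-treatment (EOT) visit only. Section 7.2.4 allows additional ECGs at other times. Section 7.2.4 and the Appendix 4 ECG footnotes also call for triplicates after an abnormal reading, but give only the spacing within the triplicate and no one-hour delay.

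**The concern.** The ECG parameters are a secondary safety endpoint (Protocol Section 2.2.2). The protocol treats one reading as not enough to act on and bases the dosing decision on a later triplicate mean. The SAP rules sort ECGs by nearness to the original and by link to a scheduled visit, and that triplicate meets neither condition. A confirmed on-treatment QTcF prolongation, which is the ECG finding a reader would most want to see, could then be missing from every ECG table. SAP 10.5.5 describes no table of QTcF threshold exceedances that would show it another way.

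**Working it through.** No sample size or power figure is involved. The check compares the timing rules and then follows the triplicate through the SAP for each place a trigger can occur.

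**Timing.** Inputs are about 60 minutes and 2 to 3 minutes spacing (Table 3) and 15 minutes (SAP 10.1.2).
- First reading: about 60 min, which is 60 − 15 = 45 min outside the window.
- Second reading: 60 + 2 to 60 + 3 = 62 to 63 min.
- Third reading: 60 + 4 to 60 + 6 = 64 to 66 min.

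All three are unscheduled when taken after dosing. The baseline exception does not help an on-treatment reading, because SAP 10.1.1 takes the Part 2 baseline from before the first Part 2 dose.

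**Where the trigger can occur.**

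| Trigger | Status of the triplicate | What the ECG summary holds | Hold or stop at stake? |
|---|---|---|---|
| Part 2, between first dose and end of treatment (0 scheduled ECGs) | No scheduled time point, whatever the delay | Neither trigger nor triplicate | Yes |
| Part 2 EOT visit | Unscheduled at about 60 min | The single reading, or a prompt repeat of it | No, drug already stopped |
| Part 2 predose visit | Predose repeat, no time limit | Can serve as baseline | Not on the summary point |
| Part 1 scheduled postdose ECG | Repeat if started at once (for example 2, 4 and 6 min); unscheduled at about 60 min | The triplicate mean or the single reading, depending on the delay | No, single dose |

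The first row carries the dosing decision, and there the 15-minute limit is not the operative cause. Even a triplicate taken within 15 minutes would be a repeat of a reading that is itself left out.

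**EOT waiver.** Section 7.3 and the Part 2 schedule footnote allow the EOT ECG to be skipped if one was done within 14 days. The SAP has no rule mapping that earlier ECG to EOT. Read literally, a patient stopped after a Table 3 triplicate could have no post-baseline ECG in the Part 2 summary.

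**Size where the window does act.** Assumed values, not from the documents: baseline 440 ms, scheduled reading 505 ms, triplicate mean 470 ms one hour later.
- Change kept in the summary: 505 − 440 = +65 ms. Change on the triplicate: 470 − 440 = +30 ms.
- Effect of one such patient on a mean change: (65 − 30)/4 = 8.75 ms with n = 4; (65 − 30)/10 = 3.5 ms with n = 10.

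This applies at most to Part 1, and there only if the triplicate is delayed and no prompt repeat replaces the original.

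**The case against.** The other side has good points, and several stand.

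- Part 2 has no planned change-from-baseline ECG summary, so the mean-change figures cannot describe it. This stands.
- Holds belong to Part 2. A scheduled EOT trigger comes after the drug has stopped, and Part 1 has only one dose. The 15-minute rule therefore never removes a reading that decides dosing and would otherwise have been summarized. This stands, and it is why the exclusion of unscheduled readings is the main cause.
- Section 7.2.4 has an out-of-range single ECG repeated once, with no delay stated. Done promptly, that repeat would replace a spurious spike. This stands for scheduled ECGs.
- The event is not hidden. Unscheduled readings stay in the listings and out-of-range values are flagged. Protocol Section 8.2 has clinically significant ECG abnormalities recorded as adverse events, generally including those that lead to dose interruption. TEAEs and disposition are summarized. This stands, although an adverse event table gives a coded term and grade, not the confirmed QTcF value.
- Table 3 is offered as general guidance that the investigator may modify, so one hour is not a fixed window. True, but an on-treatment Part 2 triplicate is left out at any delay.
- The SAP treats the first reading of a triplicate as the original, so the set might stand by itself. It would still have no scheduled time point.
- With about 4 to 10 patients and descriptive analysis only, a listing can show such a case. This limits the importance, but does not supply a summary of the thresholds the protocol acts on.

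**Conclusion.** Applied as written, the SAP keeps the triplicate behind a Part 2 hold or discontinuation out of every ECG summary. The cause in Part 2 is the exclusion of unscheduled readings, together with a schedule that has no ECG between first dose and end of treatment. The 15-minute window is a secondary fault. It acts only when the trigger is a scheduled postdose ECG: at EOT, or in Part 1 if the triplicate is delayed.

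A reader might infer more: that the 15-minute rule alone loses the deciding reading, that the event goes unreported, or that Part 2 mean changes are biased by 8.75 or 3.5 ms. The documents support none of these. Widening the window would not bring an on-treatment triplicate into a table, the listings and adverse event reporting remain, and Part 2 has no mean-change ECG summary.

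The practical size is modest. It concerns the descriptive reporting of a secondary safety endpoint in a very small study, with no effect on the PK endpoints or on the dosing decision itself. The conclusion assumes that the SAP definitions are applied literally and that the TFL shells, which are not among the documents, do not already contain a QTcF threshold table.

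**What to change.** 1. In SAP 10.5.5, add by part a count of patients with any postdose QTcF above 500 ms or more than 60 ms above the SAP 10.1.1 baseline, and of those confirmed by the triplicate mean. Use scheduled and unscheduled ECGs. This is the change that closes the Part 2 gap.
2. In SAP 10.1.2, state that a protocol-required confirmatory triplicate of a scheduled ECG counts as a repeat of that ECG whatever the delay, with its mean used for the time point and the original kept in the listing.
3. Reconcile the triplicate timing in Protocol Table 3, Section 7.2.4 and the Appendix 4 ECG footnotes. Which timing is right is for the sponsor and investigators to settle.

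The cost is one small extra table, one added SAP sentence and the protocol reconciliation. The two SAP changes need no further ECGs or data.
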